8.6. Data management

This study will use secondary data collected in the HealthVerity Healthcare database, specifically from the Vaccine and Real-Time Insights and Evidence (RTIE) data sets, which are de-identified and HIPAA compliant. The study will utilize a data cut consisting of data from December 1, 2018 through July 8, 2021 (or the most recent data available).

8.7. Data analysis

Data analyses will follow extensive feasibility analyses aimed at determining whether a full study and the assessment of vaccine effectiveness are feasible, as illustrated below:

Study implementation approach

Characteristics of the IC, non-IC and total population (IC + non-IC) groups will be described. Descriptive statistics for continuous variables will include N (number of patients), mean, median, standard deviation, Q1, Q3, minimum, and maximum. Categorical variables will be described using frequency counts and percentages.

The incidence rate of breakthrough cases of SARS-CoV-2 infection will be determined based on the following:

- Among fully vaccinated patients, those who have a claim for COVID-19 (ICD-10-CM: U07.1) that occurs on or after >14 days following their second dose of an mRNA vaccine (or 1st dose of Johnson & Johnson) will be considered to have had a breakthrough event. The time from 14 days after the qualifying dose until the breakthrough event will be the person time at risk.

PFIZER CONFIDENTIAL

- Among fully vaccinated patients with no evidence of COVID-19 after their qualifying dose, the time from 14 days after the qualifying dose until the end of follow-up will be the person time at risk.

[figure not shown]
The incidence rate of breakthrough cases of SARS-CoV-2 infection will be calculated as the number of patients who experience the event divided by the observed time at risk, and reported per 100 person years. Poisson 95% confidence intervals will be reported for the incidence rates.

Absolute effect measures such as risk difference between non-IC and IC will be reported. Time period specific effect estimates (eg, at 6 months after vaccination) may be estimated if feasible. The characteristics of the breakthrough infections will be described, including clinical presentation and severity.

The primary analysis will describe results among the non-IC cohort and the IC cohort who are vaccinated with BNT162b2. Subgroup analyses will include results for clinically meaningful subgroups as defined by vaccination type, relevant patient characteristics (eg, age), and each IC condition as listed below:

- HIV/AIDS
- Solid malignancy
- Bone marrow transplant
- Organ transplant (excluding bone marrow)
- Rheumatologic/inflammatory
- Primary Immunodeficiencies
- Other immune condition
- CKD or ESRD
- Hematologic malignancy
- IS drug use: >14 days IS medications (chemotherapy, immuno-modulators (IM), or corticosteroids excluding low-dose [<60mg/day] prednisone – See Drug List) and not falling into any of the above 9 condition groups
- >14 days of anti-metabolite use and not falling into any of the above 10 condition or drug use groups
- More than 1 IC condition

PFIZER CONFIDENTIAL

Analyses for younger cohorts (eg, 12-15) will also be conducted, as data accumulates.

For the exploratory aim, the Screening Method will be used to calculate VE for the overall study population of subjects with an IC condition and also stratified VE estimates for the different immunocompromised subject groups, with VE also determined for those subjects with >1 IC condition²⁶. We will use the proportion of the population that are vaccinated (PV) and the proportion of subjects with breakthrough SARS-CoV-2 infections that are vaccinated (PCV) to calculate VE using the following formula:

$$VE = (PV - PCV) / [PV(1-PCV)]$$

where PV = the proportion of the population that is vaccinated (ie, vaccination coverage) and PCV = the proportion of subjects with breakthrough SARS-CoV-2 infections that are vaccinated.

Additionally, breakthrough incidence rates and VE will be stratified by age at diagnosis (eg, < 65 and \geq 65 years of age at index vaccination).

Sensitivity analyses will be conducted to test the robustness of findings by varying key study design aspects (eg, continuous enrolment, IC case definition) and data analysis techniques. Other statistical techniques (eg, matched analyses, multiple regression, propensity scores) may be applied on an exploratory basis after careful examination of potential confounders (eg, age, time from vaccination). Exploratory analyses related to alternate dosing may also be conducted upon feasibility results, and as recommendations from public health authorities evolve. The analyses (entirely or in part) will be conducted over time and updated on a rolling basis as monthly data cuts become available.

While the analyses will be focused on the IC population, analyses will also be conducted (in part or entirely) on the non-IC population, the total (IC + non-IC) population or relevant subgroups (eg, other high-risk conditions, vaccination status) to support the interpretation of findings.

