8. RESEARCH METHODS

8.1. Study design

This study will be a retrospective database analysis utilizing data sets within the HealthVerity database (Philadelphia, Pennsylvania) covering the time period 01 December 2018 through 08 July 2021 (or latest data available) to describe the characteristics of subjects with IC conditions vaccinated with BNT162b2 and to evaluate the incidence of SARS-CoV-2 breakthrough infections.

Study period: 01 December 2018 – 08 July 2021 (or latest data available)

Index identification period: 11 December 2020 – 08 July 2021 (or latest data available; inclusive)

Index date: The first record for a SARS-CoV-2 vaccine (primary analysis: BNT162b2; sensitivity analyses: any Mrna, any authorized vaccine) from a medical claim, pharmacy claim, or chargemaster record.

Baseline period: 12-month period prior to the index vaccination date

Follow-up period: Variable period beginning after the index date and continuing until the earliest of the following: end of the study or end of continuous insurance enrollment.

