8.2. Setting

The primary analysis of this study will include all people at least 12 years of age with at least one vaccine claim (primary analysis: BNT162b2; sensitivity analyses: any Mrna, any authorized vaccine) between 11 December 2020 and 08 July 2021 (or latest date available) from the HealthVerity HealthCare Database. Patients included in the study will be required to have 12 months of continuous medical enrollment prior to the receipt of their first vaccine and have no evidence of a SARS-CoV-2 infection in the year prior to being vaccinated.

The study population will be stratified into two cohorts: non-immunocompromised and immunocompromised. Patients with IC conditions will be identified using a modified implementation of an algorithm developed by Greenberg et al – and later modified and

expanded by Patel et al – for administrative claims based on claims and healthcare records identified in the 12 month baseline period.^{24, 25}

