8.2.1. Inclusion criteria

Patients must meet all of the following inclusion criteria to be eligible for inclusion in the study:

1. Unique enrollees in the HealthVerity Vaccine dataset any time **after** 10 December 2020
2. At least 12 years on the index date (ie, first vaccination date)
3. No evidence of prior COVID-19 infection (a medical claim, pharmacy claim, or chargemaster record with an International Classification of Diseases, 10th Revision, Clinical Modification (ICD-10-CM) diagnosis code of U07.1) in the 12 months prior to the index date
4. Have 12 months of continuous enrollment with medical benefits (with or without pharmacy benefits) prior to the index date

Subjects with an IC condition were identified via an algorithm originally developed and validated by Greenberg et al²⁴ for use in administrative claims database studies. For this study, this algorithm will be modified and expanded based on expert medical opinion. The algorithm is depicted in [Figure 1](#).

Subjects will be identified as immunocompromised if they had ≥ 1 hospitalization or ≥ 2 outpatient visits on separate dates with an ICD-10-CM code on a healthcare claim indicating an IC condition or if they had usage of specific immunosuppressive medications during the 12-month baseline period. The IC case definition will incorporate 8 groups based on clinical diagnoses only, 1 group based on both clinical diagnoses and usage of immunosuppressive medication, and 2 other groups based on usage of immunosuppressive medication only, for a total of 11 groups with an IC condition ([Figure 1](#)). Subjects with >1 IC condition will also be assessed, for a total of 12 mutually exclusive groups for inclusion in this study. The list of ICD-10-CM codes used to identify IC cases by diagnosis and list of immunosuppressive medications are shown in the Annex.

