8.3. Variables

Table 1. Immunocompromising Conditions definition

Variable	Role	Data source(s)	Operational definition
Immunocompromising Conditions	Cohort Definition	HealthVerity Vaccine Data	
Subjects will be categorized into the following 12 mutually exclusive IC groups based on the algorithm detailed in Figure 1:
 
Symptomatic HIV/AIDS, solid malignancy, bone marrow transplant recipients, organ transplant recipients, rheumatologic or other inflammatory conditions, primary immunodeficiencies, other intrinsic immune conditions, chronic kidney disease or end stage renal disease, hematologic malignancy, immunosuppressive treatment only, antimetabolites only, or >1 IC condition.

PFIZER CONFIDENTIAL

Table 1. Immunocompromising Conditions definition

Variable	Role	Data source(s)	Operational definition
			
Subjects falling into more than one of these categories will be categorized as having >1 IC condition.
 
At a minimum, subjects will be required to have one inpatient claim or two outpatient claims on separate days with the IC condition of interest in the baseline period. In cases when >14 days of treatment are required it will be based on the dispensed day supply or distinct days of treatment in the baseline period.
 
The main diagnosis codes to identify IC conditions are presented in ANNEX 1. LIST OF STAND ALONE DOCUMENTS.

Table 2. Vaccination Status definitions

Variable	Role	Data source(s)	Operational definition
Any vaccination	Cohort Definition	HealthVerity Vaccine Data	
Patients with a claim for any vaccine will be considered vaccinated with any vaccine based on the following codes:
 
Pfizer/BioNTech: 91300, 0001A, 0002A, 59267100001, 59267100002, 59267100003
 
Moderna: 91301, 0011A, 0012A, 80777027310, 80777027399, 80777027315, 80777027398
 
Johnson & Johnson: 91303, 0031A, 59676058005, 59676058015
 
Source: https://www.cdc.gov/vaccines/programs/iis/COVID-19-related-codes.html

Fully Vaccinated	Cohort Definition	HealthVerity Vaccine Data	
Patients will be considered fully vaccinated if they meet any of the following definitions:
 
Two claims for Pfizer/BioNTech vaccine on separate days with >14 days of follow-up after the 2nd vaccination date. No claims for any other vaccines are allowed.

PFIZER CONFIDENTIAL

Table 2. Vaccination Status definitions

Variable	Role	Data source(s)	Operational definition

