Other baseline medication use	Patient Characteristics	HealthVerity Vaccine Data	Medications for pre-existing conditions per the Sentinel COVID-19 Natural History Master Protocol (eg, angiotensin converting enzyme inhibitors (ACE), angiotensin-receptor blockers (ARB)).
Vaccine utilization	Patient Characteristics	HealthVerity Vaccine Data	Patterns of uptake. The proportion of IC and non-IC patients who are partially and fully vaccinated with BNT162b2 (or any other vaccines), at different calendar months and follow-up periods (eg, 7 days post dose 2, 14 days post dose 2). Mean, median, minimum, and maximum time between receipt of the first and second dose of BNT162b2 (or any other vaccine)

Table 4. Breakthrough Cases Definition

Variable	Role	Data source(s)	Operational definition
Breakthrough SARS-CoV-2 infection	Outcome	HealthVerity Vaccine Data	Among patients who meet the definition of fully vaccinated, a breakthrough SARS-CoV-2 infection will be defined by evidence of a claim with a diagnosis code of U07.1 that occurs >14 days after the second vaccination date. The first claim with a diagnosis of COVID-19 after this time will be used to assess mean and median time from the second dose until the breakthrough case

PFIZER CONFIDENTIAL

Table 5. COVID-19 Healthcare resource use and Costs definitions

Variable	Role	Data source(s)	Operational definition
Emergency department (ED) visit	Outcome	HealthVerity Vaccine Data	An outpatient claim with a place of service = 23 that occurs after the breakthrough COVID-19 diagnosis date or at the same time/episode of care
Outpatient Hospital Visit	Outcome	HealthVerity Vaccine Data	An outpatient claim with a place of service = 22 or 19 or a standard billing code that begins with '13' that occurs after the breakthrough COVID-19 diagnosis date or at the same time/episode of care
Other Outpatient Visit (not ED, not hospital-based)	Outcome	HealthVerity Vaccine Data	An outpatient claim that does not meet the definition for an ED visit or Outpatient hospital visit.
Hospitalization	Outcome	HealthVerity Vaccine Data	A record from the chargemaster data with encounter type of Inpatient OR a series of claims (separated by no more than 2 days) with a place of service = 21 or standard billing codes that begin with '11' or '12' that occur after the breakthrough COVID-19 diagnosis or at the same time/episode of care 1 st admission and readmissions will be differentiated.

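### Prior infection is screened only before dose 1, so a later claim for an infection already recorded by day 14 after the qualifying dose counts as a breakthrough

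*Combined protocol and SAP*

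**What the plan says.** **Screen for prior infection.** Section 8.2 requires that subjects "have no evidence of a SARS-CoV-2 infection in the year prior to being vaccinated". Inclusion criterion 3 in section 8.2.1 makes this the absence of a U07.1 record "in the 12 months prior to the index date". Section 8.1 defines the index date as "The first record for a SARS-CoV-2 vaccine", that is, dose 1.

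**Fully vaccinated.** For BNT162b2, Table 2 (section 8.3) asks for "Two claims for Pfizer/BioNTech vaccine on separate days with >14 days of follow-up after the 2nd vaccination date" and no claim for another vaccine. It sets no condition on infection.

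**Event.** Section 8.7 counts "those who have a claim for COVID-19 (ICD-10-CM: U07.1) that occurs on or after >14 days following their second dose", or the same interval after the single Johnson & Johnson dose. Table 4 uses the same rule and dates the event by the earliest U07.1 record past that point: "The first claim with a diagnosis of COVID-19 after this time will be used to assess mean and median time from the second dose".

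**Person-time.** Section 8.7 has two bullets. Cases contribute time from 14 days after the qualifying dose to the event. Time to the end of follow-up is given to the others only if they are "Among fully vaccinated patients with no evidence of COVID-19 after their qualifying dose".

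**Severity.** Table 5 takes hospital stays "that occur after the breakthrough COVID-19 diagnosis or at the same time/episode of care". ICU use and death are likewise anchored on the breakthrough diagnosis.

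**The concern.** One infection can generate several claims over weeks. If the first falls between dose 1 and day 14 after the qualifying dose, the screen does not see it because it comes after the index date. The event rule does not see it either, because it looks only at claims after day 14. A later claim for the same illness is then taken as a new breakthrough.

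This rule defines the Aim 2 event and the Aim 3 case series. Carry-over claims would raise the breakthrough rate, shorten the time to infection and bring earlier episodes into the hospitalization, ICU and death results.

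Whether the carry-over share differs between IC and non-IC subjects is unknown, so no bias in the risk difference between them is claimed.

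**Working it through.** **Step 1: trace the rules.** The plan states no rate, event count or sample size, so there is no figure to reproduce. The text gives the following for fully vaccinated subjects:

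| U07.1 history | Treatment under the plan |
|---|---|
| Claim in the 12 months before dose 1 | Excluded |
| Claim between doses, none later | Stays in the denominator as at risk |
| Claim between doses, another after day 14 | Breakthrough |
| Only claim on days 1-14 after the qualifying dose | Fits neither person-time bullet |
| Claim on days 1-14, another after day 14 | Breakthrough |

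For Johnson & Johnson the unscreened window is only the 14 days after the single dose.

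**Step 2: inputs for the size (all assumed).**
- Dose interval 21 days, then 14 days.
- Mean time at risk 0.3 year (109.6 days), varied from 0.2 to 0.45. With the 8 July 2021 cut, the longest possible is 209 days from 11 December 2020, less 35, or 174 days (0.48 year).
- q: share of those infected between doses who still receive dose 2.
- cA, cB: share of infections between doses, and on days 1-14 after dose 2, with a further U07.1 claim after day 14.
- R: window infection rate divided by true breakthrough rate r2. The window rate is r = R × r2.

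**Step 3: inflation of the rate.** With A = 1 − exp(−r × 21/365.25) and B = 1 − exp(−r × 14/365.25):
- false events per subject = A × q × cA + B × cB
- true events per subject = 1 − exp(−r2 × 0.3)

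For small rates, inflation per unit of R is (14 × cB + 21 × q × cA) / 109.6:
- Low (q 0.5, cA 0.025, cB 0.05): (0.70 + 0.26)/109.6 = 0.88%
- Middle (q 0.75, cA 0.05, cB 0.10): (1.40 + 0.79)/109.6 = 2.0%
- High (q 1, cA 0.10, cB 0.20): (2.80 + 2.10)/109.6 = 4.47%

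The exact form at r2 = 0.01 per year, with middle inputs, gives 0.6, 1.8, 3.0 and 6.0 false events per 10,000 at R = 1, 3, 5 and 10, against 30 true ones. At 0.2 or 0.45 year at risk, the middle figure is 3.0% or 1.3% per unit. Infections on days 1-14 alone give 0.6%, 1.3% and 2.6% (low, middle, high).

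**Step 4: time to infection.** Suppose that false events fall evenly on days 15-30 and true events evenly over 110 days from day 15. With inflation f, the median m solves (m − 15)/110 + f × min((m − 15)/15, 1) = (1 + f)/2. The false share of events on days 15-30 is f/(f + 15/110). With no inflation the median is 70 days.

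| R | Inflation, low to high | Inflation, middle (f) | Median from dose 2 at middle f | False share of events on days 15-30 at middle f |
|---|---|---|---|---|
| 1 | 0.9-4.5% | 2% | 68.9 days | 13% |
| 3 | 2.6-13% | 6% | 66.7 days | 31% |
| 5 | 4.4-22% | 10% | 64.5 days | 42% |
| 10 | 8.8-45% | 20% | 59.0 days | 59% |

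**Step 5: a second set of assumptions.** Take 100,000 subjects, a 35-day window, 3 window infections per 100 person-years, a true rate of 0.5 to 1.0 per 100 person-years and 60 to 120 days at risk. If 5% of window infections have a later claim, there are 100,000 × 0.03 × 35/365.25 × 0.05 = 14 false events, or 4% to 15% of counted breakthroughs. At 20% there are 57, or 15% to 41%. The direction is the same, and the size again depends on the inputs.

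**The case against.** The strongest objection concerns size. Every input is assumed, and the 0.9% to 45% range arises largely because the ratio R is varied from 1 to 10 with nothing in the documents to anchor it. At ratio 1 the middle effect is 2% and the median moves by about one day. The shares on days 15-30 follow from the assumed placement of false and true events. The between-dose part is the weaker one: an infection soon after dose 1 needs a claim about five weeks later to count. All of this stands, and it limits what can be said about size, though not about the rule.

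The plan also has partial safeguards:
- Section 8.9 acknowledges misclassification in claims data in general terms.
- Section 8.7 leaves its list of sensitivity analyses open, although its examples do not include this one.
- Table 5 joins hospital claims no more than 2 days apart and separates first admissions from readmissions. A stay that began before day 15 could therefore be recognised.

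None of these changes which claim counts as an event. Whether such a stay would be counted depends on how inpatient claims are dated, which is not stated.

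The subject who fits neither person-time bullet may simply be meant to drop out. That reading is natural but unwritten, and it does not reach the event bullet, which has no such condition.

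Finally, section 8.5 calls the study mainly descriptive, and no test or decision threshold depends on this rate. That is correct, but the rate, the time to infection and the severity results are the study's primary outputs.

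**Conclusion.** The concern holds. As written, the event rule turns a later claim for an infection already recorded between dose 1 and day 14 after the qualifying dose into a breakthrough, and no other section prevents it. The direction is certain, since carry-over claims can only add events.

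The size cannot be fixed from the documents. It is small overall if infection was about as frequent in the window as the true breakthrough rate, and grows in proportion if infection was more frequent then. Under any of these inputs it is concentrated in the earliest breakthroughs, provided carry-over claims come soon after day 14. This should be corrected because it sits in the primary definition for Aims 2 and 3 and the data needed are already held.

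**What to change.** In Table 4 and section 8.7, start risk on day 15 after the qualifying dose, and only in subjects with no U07.1 claim from the index date through day 14 after that dose. Remove the others from both events and person-time. This uses only information from before risk time starts, and it settles the subject who now fits neither person-time bullet. Report the number removed by IC status, and report the rate under the current rule as a sensitivity analysis so that the actual size is seen.

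The cost is a few lines of text. The share removed is A × q + B. With q from 0.5 to 1 it is 0.07% to 0.2% of subjects at assumed window rates of 1 to 2 per 100 person-years, and 0.3% to 1.9% at 5 to 20. Any true later infection in those subjects is lost, and the target group becomes those with no recorded infection through day 14.

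Infections first claimed after day 14 would remain. An episode or washout rule is an alternative, but it needs its own cut-off.

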immune response to the COVID-19 mRNA vaccines in people with an IC condition leads to reduced VE. In the RCTs of the mRNA vaccines, those with an IC condition were largely excluded from the study populations.^{13, 14} A few recently conducted real-world studies that contained subpopulations with IC conditions have found that while the COVID-19 vaccines were effective in this patient group, VE against SARS-CoV-2 infection, symptomatic illness, and COVID-19-related hospitalization was lower than observed in the general populations of these studies.¹⁵⁻²³

On 12 August 2021, the FDA amended the EUA for the mRNA COVID-19 vaccines to allow for the use of an additional dose for certain immunocompromised subjects with moderate to severe IC conditions. According to the Centers for Disease Control and Prevention (CDC) guidelines (COVID-19 Vaccines for Moderately to Severely Immunocompromised People | CDC), the additional dose should be administered at least 28 days following the two-dose regimen of the same vaccine to individuals 18 years of age or older (ages 12 or older for Pfizer-BioNTech) who have undergone solid organ transplantation, or who are diagnosed with conditions that are considered to have an equivalent level of immunocompromise. A third dose of the same Mrna vaccine should be used; however, if the Mrna vaccine product given for the first two doses is not available or is unknown, either Mrna COVID-19 vaccine product may be administered.

Further study of patients with various IC conditions is warranted to gain a better understanding of which IC conditions may predispose people to reduced COVID-19 VE to guide further prevention efforts.

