7. RESEARCH QUESTION AND OBJECTIVES

The overall objective of this study is to evaluate characteristics, vaccine utilization and outcomes among vaccinated subjects with IC conditions. The primary analysis will be conducted on subjects vaccinated with BNT162b2. A variety of subgroup analyses are planned, along with multiple sensitivity analyses that will test how variations in study design affect results.

Primary Objectives:

Aim 1: Describe profiles, vaccine utilization and resource use among subjects with IC conditions vaccinated with BNT162b2

Aim 2: Evaluate incidence rates of breakthrough infections among subjects with IC conditions fully vaccinated with BNT162b2

Aim 3: Evaluate the clinical presentation of vaccine breakthrough cases among subjects with IC conditions, including time to infection and severity of disease (hospitalization, mortality)

Secondary Objectives

Evaluate Aims 1, 2, 3 and HCRU/costs over time and stratified by relevant patient characteristics (eg, age), in specific IC conditions and by vaccination type (eg, any Mrna).

Exploratory Objective

Generate early estimates of the effectiveness of BNT162b2 in preventing COVID-19 infection, stratified by relevant patient characteristics (eg, age), in specific IC conditions.

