Prevention seeking behavior (at baseline)	Patient Characteristics	HealthVerity Vaccine Data	
These variables will be assessed during the 12 month baseline period:
 
Telephone or Telehealth visits defined as a claim with any of the following procedure codes (G2012, G2010, G2061-G2063; 99205-99205, 99212-99215, 99421-99423, 99441-99443, G0425-G0427, G0406-G0408)
 
COVID-19 laboratory tests defined as a claim with any of the following CPT-4 codes (87635, 86318, 86328, 86769, 87426, 86408, 86409, 86413)
 
Flu vaccinations defined as a claim with the following procedure codes (90653-90664, 90666-90668, 90724, 90470, 90672, 90673, 90685-90688)
 
The cumulative proportion of IC and non-IC subjects receiving their first dose of COVID-19 vaccine, by month, starting from December 2020 until most recent data.

Acute Respiratory Infection Hospitalization (at baseline)	Patient Characteristics	HealthVerity Vaccine Data	Any inpatient claim that occurs in the 12 month baseline period with a diagnosis of J00-J06, J09-J18, J20-J22 will be reported
Follow-up time	Patient Characteristics	HealthVerity Vaccine Data	The number of days between the index date and the earliest of the following: end of the study or end of continuous insurance enrollment
IS drugs use	Patient Characteristics	HealthVerity Vaccine Data	The proportion of subjects with IC conditions and usage of IS drugs for >14 days during the baseline period will be reported, as well as use within 14 days and 28 days within receipt of the first vaccine dose. IS drugs exclude low-dose [<60mg/day] prednisone.

PFIZER CONFIDENTIAL

Table 3. Patient Characteristics and Vaccine Utilization variable definitions

Variable	Role	Data source(s)	Operational definition
COVID-19 supportive medication use	Patient Characteristics	HealthVerity Vaccine Data	The use of medications considered supportive for COVID-19 will be assessed in the 12-month baseline period including remdesivir, dexamethasone, doxycycline, norepihephrine, methylprednisolone, lopinavir/ritonavir, eculizumab, sarilumab, tocilizumab, losartan, azithromycin, hydroxychloroquine, siltuximab, colchicine, and convalescent plasma. Codes used to identify these treatments will be based on the Sentinel COVID-19 Natural History Master Protocol

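### Table 2's ban on other-vaccine claims has no time limit, so at later data cuts a further dose can delete at-risk time and breakthroughs that came before it

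*Combined protocol and SAP*

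**What the plan says.** Aim 2, a primary objective in section 7, is to "Evaluate incidence rates of breakthrough infections among subjects with IC conditions fully vaccinated with BNT162b2". Table 2 in section 8.3 defines that status for BNT162b2 by "Two claims for Pfizer/BioNTech vaccine on separate days", with more than 14 days of follow-up after the second, and adds "No claims for any other vaccines are allowed". The Moderna and Johnson & Johnson definitions carry the same ban. None ties it to a date. A subject excluded by it does not become partially vaccinated either, because that class requires a single claim and no other vaccine.

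Section 8.7 sets the denominator. For subjects without a breakthrough, "the time from 14 days after the qualifying dose until the end of follow-up will be the person time at risk". Section 8.1 has follow-up "continuing until the earliest of the following: end of the study or end of continuous insurance enrollment", and Table 3 repeats this: "The number of days between the index date and the earliest of the following: end of the study or end of continuous insurance enrollment". Table 4 counts a breakthrough on any U07.1 claim more than 14 days after the second dose. A further dose changes none of these.

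Section 6 shows that further doses were foreseen: "On 12 August 2021, the FDA amended the EUA for the mRNA COVID-19 vaccines to allow for the use of an additional dose". The change reaches only some people with IC conditions. The section adds that either mRNA product may be given when the first is unavailable or unknown. The dated cut is 08 July 2021 or the latest data available, and section 8.7 plans rolling updates at monthly cuts. Section 8.7 also allows optional exploratory analyses of alternate dosing.

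**The concern.** A subject can complete two BNT162b2 doses, contribute months of at-risk time, perhaps have a breakthrough, and then receive another brand. Under Table 2 as written that subject was never fully vaccinated, and everything already observed is dropped. Eligibility at the start of at-risk time should not depend on what happens later.

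The unmarked dose count creates a second fork. Elsewhere the protocol marks minimums explicitly, for example two or more outpatient visits in section 8.2.1. Here a programmer could choose either reading: one removes same-brand third-dose recipients, the other keeps them and counts their later time and events. These are different rates, and the choice could change what Aim 2 means from one monthly cut to the next.

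The comparison is exposed too, since "Absolute effect measures such as risk difference between non-IC and IC will be reported". The amendment in section 6 concerns immunocompromised people, so the IC rate could move more than the non-IC rate.

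**Working it through.** The plan states no expected rate, uptake or event count, so there is no figure to reproduce. The sizes below are illustrative.

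**Dates from the documents**
- 08 July to 12 August 2021 is 35 days, so the dated cut precedes the amendment.
- 08 July to the planned analysis start of 25 August is 48 days. If that lag recurred (an assumption), the interim report of 23 September would use data to 06 August, also before the amendment. An analysis ending 30 December would use data to 12 November.

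**Assumptions, none from the documents**
- At-risk time starts on average on 16 March 2021 and the hazard is constant.
- Uptake U is 10-20% of the IC cohort, linear from 12 August to the cut.
- The rate ratio RR after the further dose is 0.5 to 0.2, and the non-IC cohort is unaffected.
- f is recipients' earlier rate divided by others' rate.

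**Removal compared with censoring**

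Ratio of rates = (PTn + PTr) / (PTn + f × PTr), where PTn is non-recipients' time and PTr is recipients' time before the further dose.

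- Cut 08 July (114 days), 1% with an other-brand claim at mid follow-up on average, f = 0: (112.86 + 0.57) / 112.86 = 1.005.
- Cut 12 November (241 days, recipients' earlier time 241 − 46 = 195 days), 1% other-brand, f = 0: (238.59 + 1.95) / 238.59 = 1.008.
- Cut 12 November with two claims read as exactly two:

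| U | PTn | PTr | f = 1 | f = 0.5 | f = 0 | f = 2 |
|---|---|---|---|---|---|---|
| 10% | 216.9 | 19.5 | 1.00 | 1.04 | 1.09 | 0.92 |
| 20% | 192.8 | 39.0 | 1.00 | 1.09 | 1.20 | 0.86 |

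For example, at U = 20% and f = 0.5: 231.8 / (192.8 + 19.5) = 1.09. The direction depends on f: the rate rises only if removed subjects had fewer earlier breakthroughs than the others.

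**Counting time after the further dose (at-least-two reading)**

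Share of IC person-time after the dose = U × (P/2) / F, where P is days from 12 August to the cut and F is days from 16 March to the cut. The relative fall in the rate, against the rate up to a further dose, is share × (1 − RR).

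- Cut 12 November (P = 92, F = 241): share 1.9-3.8%. Fall from 0.0191 × 0.5 = 1.0% to 0.0382 × 0.8 = 3.1%.
- Data to 30 December, the upper limit (P = 140, F = 289): share 2.4-4.8%, fall 1.2-3.9%.
- Average start one month earlier or later, 12 November cut: 0.9-3.5%.
- If the true IC/non-IC rate ratio is 3.0 (assumed), the difference shrinks by the fall × 3/(3 − 1): 1.4-4.6% at 12 November and 1.8-5.8% at 30 December.

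**The case against.** A reader might infer that section 8.7 has no rule for person-time after a further dose. The documents do not support that. Sections 8.7, 8.1 and Table 3 together run the clock to study end or disenrolment, which on the at-least-two reading gives a rate regardless of later doses. That is a coherent target, so making the censored rate primary is partly a preference.

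Censoring may also gain little. Suppose recipients have twice others' underlying rate, and take as benchmark the cohort's rate had nobody received a further dose. In the 12 November model with U = 10% and RR = 0.5, the benchmark is 0.9 + 0.1 × 2 = 1.1. Censoring gives (216.9 + 39) / 236.4 = 1.082, or −1.6%. Not censoring gives (216.9 + 39 + 4.6) / 241 = 1.081, or −1.7%. At U = 20% the figures are −2.6% against −3.2% (RR 0.5) or −5.1% (RR 0.2). If recipients' rate equals that of others, censoring is unbiased.

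The study is also mainly descriptive, and the size is modest. A Poisson 95% half-width of 3.05% needs about (1.96/0.0305)² ≈ 4,100 events, and one of 0.95% about 42,600. The assumed uptake covers a broad IC cohort, whereas section 6 limits the additional dose to certain subjects with moderate to severe conditions.

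All of this stands, and it limits the point on counting later time to naming the primary rate. It does not answer the Table 2 defect: the undated ban is a stated rule that selects on the future, and the optional dosing and sensitivity analyses do not alter it.

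**Conclusion.** The defect in Table 2 holds: an undated ban lets a later claim erase earlier at-risk time and events, and the unmarked dose count leaves same-brand third doses either removed or counted.

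Two stronger inferences fail. Nothing shows that results at the 08 July 2021 cut are materially affected: the additional-dose effect there is nil, and the other-brand effect is at most about 1.005 times if 1% have such a claim. Nor does removal necessarily inflate the rate, since its direction depends on recipients' earlier rate.

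For cuts after 12 August 2021, with 10-20% uptake assumed, removal on the exactly-two reading gives 1.00-1.09 times when recipients' earlier rate is equal to or half that of others. Counting later time lowers the IC rate by about 1-3% at a 12 November cut. These sizes rest wholly on assumed uptake, timing and rate ratios. The text should be changed before any cut after 12 August 2021 is analysed. This concerns analysis rules only and takes no position on dosing.

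**What to change.** - **Table 2:** apply the other-vaccine ban only to claims up to the start of at-risk time, 14 days after the qualifying dose. State that two claims means at least two, and that a later claim removes neither the subject nor earlier person-time.
- **Section 8.7:** for cuts after 12 August 2021, report the Aim 2 rate both censored at the first distinct further COVID-19 vaccine dose of any brand and regardless of later doses. Name the primary one in advance.
- **Claims handling:** pre-specify how re-billed claims for the same dose are removed, and how a further claim inside the 14-day window is treated. Doses come from medical, pharmacy and chargemaster records, and section 8.8 says adjudication status is mixed. Without such a rule, a re-billed second dose could end at-risk time at any cut. For same-brand claims, the 28-day interval cited in section 6 is one possible anchor; other-brand claims need their own rule.
- **Sections 8.1 and Table 3:** leave general follow-up unchanged, so that Aims 1 and 3 are not truncated.

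The cost is short text in two places, the claims-handling rules, and a second rate at later cuts. The censored rate has slightly less person-time and may be informatively censored if more severely immunocompromised subjects leave earlier. The paired uncensored rate and the IC-condition strata help to show this.
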